### **LIST OF ABBREVIATIONS**

AE Adverse event

CI Confidence Interval

CRF Case Report Form

CTRS Clinical Trial Registry Summary

ELISA Enzyme-linked immunosorbent assay

ES Exposed Set

GMC Geometric mean antibody concentration

GSK GlaxoSmithKline

IU/mL International units per milliliter

LL Lower Limit of the confidence interval

MedDRA Medical Dictionary for Regulatory Activities

NA Not Applicable

PD Protocol Deviation

PPS Per-Protocol Set

SAE Serious adverse event

SAP Statistical Analysis Plan

SBIR GSK Biologicals Internet Randomization System

SD Standard Deviation

SDTM Study Data Tabulation Model

UL Upper Limit of the confidence interval

# Version history

SAP Version	Approval Date	Protocol Version (Date) on which SAP is Based	Change	Rationale
SAP	23 SEP 2021	10 May 2021	Not Applicable	Original version
SAP amendment 1	15 Nov 2021	10 May 2021	Addition of sensitivity analysis	Amendment 1: FDA request

## 1. INTRODUCTION

The purpose of this SAP is to describe the planned statistical analyses for Study RSV OA=ADJ-009 (217131).

## 1.1. Objectives, Estimands and Endpoints

[figure not shown]
	Objectives	Endpoints		
	Prin	mary		
•	To demonstrate the lot-to-lot consistency of 3 lots of the RSV PreFusion protein 3 Older Adult (RSVPreF3 OA) investigational vaccine in terms of immunogenicity.		RSVPreF3-specific immunoglobin (Ig)G antibody concentrations expressed as group geometric mean concentration (GMC) ratio at 30 days post-vaccination (Day 31).	
		•		
Ŀ	To evaluate the humoral immune response of the 3 lots of the RSVPreF3 OA investigational vaccine.		RSVPreF3-specific IgG antibody concentrations expressed as mean geometric increase (MGI) at 30 days post-vaccination (Day 31).	
•	To evaluate the safety and reactogenicity following administration of the RSVPreF3 OA investigational vaccine.	•	Percentage of participants reporting each solicited event with onset within 4 days after study intervention administration (i.e. the day of vaccination and 3 subsequent days).  Percentage of participants reporting unsolicited adverse events (AE) within 30 days after study intervention administration (i.e. the day of vaccination and 29 subsequent days).  Percentage of participants reporting serious AEs after study intervention administration (Day 1) up to study end (6 months after vaccination).  Percentage of participants reporting potential immune-mediated diseases after study intervention administration (Day 1) up to study end (6 months after vaccination).	
		iary		
CCI	respiratory syncytial virus			

RSV: respiratory syncytial virus.

## Primary estimand

The primary scientific question is to show equivalence of 3 lots of the RSV PreFusion protein 3 Older Adult (RSVPreF3 OA) investigational vaccine in terms of immunogenicity 1 month after vaccination in eligible participants who complied with the study requirements as defined per protocol (refer to section 3 for the definition of the per protocol set used for the primary analysis and to section 4.2 for the statistical methods).

## 1.2. Study Design

AE: adverse event; Grp: group; N: number of participants; pIMD: potential immune-mediated disease; RSV: respiratory syncytial virus; SAE: serious adverse event

BS: blood samples. Blood samples will be collected from all participants at Visit 1 and Visit 2 to assess humoral immune response.

Note: All SAEs related to study participation or a GSK concomitant medication/vaccine are to be recorded from the time the participant consents to participate in the study (prior to study vaccination) up to study end.

Design Features	The current study is designed as a phase 3, double-blind study to assess lot-to-lot consistency in terms of immunogenicity and evaluate safety and reactogenicity of the 3 RSVPreF3 OA investigational vaccine lots in adults ≥ 60 YOA. There are 3 parallel investigational groups (RSVPreF3_Grp1, RSVPreF3_Grp2, RSVPreF3_Grp3)
Study intervention	Participants will receive 1 dose of the RSVPreF3 OA investigational vaccine at Day 1.
Study intervention Assignment	Approximately 750 eligible participants will be randomly assigned to 3 study groups in a 1:1:1 ratio (approximately 250 participants in each group)
Interim Analysis	There is no interim analysis planned for this study
Final analysis	A final analysis will be conducted once all the immunogenicity data are available for the primary endpoint. This final analysis will include immunogenicity and safety data up to Visit 2 (Day 31).
End-of-study analysis	An end-of-study analysis with all data including the data obtained until 6 months post-vaccination will be performed

## 2. STATISTICAL HYPOTHESES

The study includes 1 confirmatory primary objective.

To demonstrate the lot to lot consistency of 3 lots of the RSV PreFusion protein 3 Older Adult (RSVPreF3 OA) investigational vaccine in terms of immunogenicity.

## **Null hypothesis vs. Alternative hypothesis:**

At least 2 of the 3 vaccine lots differ by more than 1.5-fold with respect to their GMCs ratio

$$H_0$$
:  $|\mu A/\mu B| > 1.5$ 

vs. Clinical equivalence (consistency) between each pair of the 3 lots with respect to their GMCs ratio

$$H_{a:} |\mu A/ \mu B| \le 1.5$$

where  $\mu A$  and  $\mu B$  representing geometric mean of IgG specific antibody concentration at day 31 (30 days post vaccination) after the RSVPreF3 OA investigational vaccine dose in vaccines lots A and B respectively and 1.5, the equivalence margin.

The null hypothesis will be rejected if the 2-sided 95% confidence interval (CI) of the GMC ratios between each pair of the 3 lots is within the pre-defined clinical limit of [0.67, 1.5].

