9. STATISTICAL CONSIDERATIONS

9.1. Statistical hypotheses

The assumptions, statistical hypotheses and success criteria associated to the primary objective to demonstrate the lot-to-lot consistency of 3 lots of the RSVPreF3 OA investigational vaccine in terms of immunogenicity at 30 days post-vaccination are described hereafter.

- **Endpoint:** RSVPreF3 IgG-specific antibody concentration at 1-month post-vaccination (Day 31).
- **Group level summary:** Antibody GMC per group.
- Reference for the sample size calculation: A standard deviation (SD) of the log₁₀ transformed concentrations of 0.45 is used as reference. It is the highest SD observed in the RSV OA=ADJ 002 (208851) study among all treatment groups and humoral assays.
- Success criteria for consistency: the 2 sided 95% confidence interval (CI) of the GMC ratios between each pair of the 3 lots is within the pre-defined clinical limit of [0.67, 1.5].
- **Null hypothesis:** At least 2 of the 3 vaccine lots differ by more than 1.5-fold (1 sided non-inferiority limit) with respect to their GMC.
- **Alternative hypothesis:** Clinical equivalence (consistency) between each pair of the 3 lots with respect to their GMCs.
- **Type I error:** a 1-sided alpha of 2.5% will be used for the 6 non-inferiority tests.
- **Type II error:** Considering a Bonferroni correction for multiplicity, the global Type II error will be equal to 6 time the nominal Type II error calculated for 1 non-inferiority test. The sample size is determined to reach a global power of at least 90%.

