9.3.1. Primary endpoint analysis

The primary analysis of lot-to-lot consistency will be performed on the PPS for immunogenicity (PPSi).

If in any study group the percentage of vaccinated participants with serological results excluded from the PPSi is more than 5%, a second analysis based on the Exposed Set (ES) will be performed to complement the PPSi analysis.

The 3 RSVPreF3 OA investigational vaccine lots will be compared in terms of RSVPreF3 IgG-specific antibody concentrations at 1-month post-vaccination, with a 1-sided alpha of 2.5%. The 95% CIs of the GMC ratios will be computed for each pair of RSVPreF3 OA investigational vaccine lots (RSVPreF3_Grp1 versus RSVPreF3_Grp2, RSVPreF3_Grp1 versus RSVPreF3_Grp3, RSVPreF3_Grp2 versus RSVPreF3_Grp3) using an analysis of covariance (ANCOVA) model on the log transformation of the RSVPreF3 IgG concentrations. The ANCOVA model will include the vaccine group and the age category (60 to 69 years, 70 to 79 years, \geq 80 years) as fixed effect and the baseline antibody concentration as covariates.

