## 2.1. Multiplicity Adjustment

A 1-sided alpha of 2.5% will be used for the 3 equivalence tests.

No adjustment of Type 1 error is needed because all the Lot to Lot consistency criteria must be met simultaneously.

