### 4. STATISTICAL ANALYSES

## 4.1. General Considerations

## 4.1.1. General Methodology

Confidence intervals will use 95% confidence levels.

The group GMC ratio will be based on a back transformation of group contrast in an ANCOVA model applied to the logarithm- transformed titers.

Primary analysis: The ANCOVA model will include the treatment group and the age category (age at vaccination: 60-69, 70-79 or ≥80 years) as fixed effects and the pre-dose log-10 titer as covariate.

Sensitivity analysis: The ANCOVA model will include the treatment group and the age category (age at vaccination: 60-69, 70-79 or ≥80 years) and the center as fixed effects and the pre-dose log-10 titer as covariate.

95% CI for GMC will be based on a back transformation of CI for the mean of log-transformation.

The equivalence will be shown if the 95% CIs of the geometric mean concentration (GMC) ratio of each lot over the each other lot is inside the acceptance limit 0.67-1.5 for the antibody concentration 30 days post vaccination (day 31).

95% CI for proportion will be based on exact [Clopper,1934] Pearson CI.

Summary results will be presented by group for immunogenicity and safety and by group and in total for demographic characteristics (pooling of the 3 groups).

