\* SD = 0.45 was selected based on the results from the RSV OA=ADJ-002 study. A conservative approach was used by selecting the highest value observed for SD across groups and humoral assays.

The primary objective analysis will be performed on the PPS. Assuming a 10% non-evaluable rate up to Day 31 (participants dropped-out or excluded from the PPS), a total of 750 participants (250 per group) will have to be enrolled in order to reach 225 participants evaluable for the primary objective.

Secondary Objectives: NA

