## 6.2.4.3. Serological summary statistics

For each assay, geometric mean titers (GMT) or concentrations (GMC) and their confidence limits will be presented with one decimal, as well as GMT/GMC fold increase from pre-dose.

GMT or GMC group ratios and their confidence limits will be displayed with 2 decimals regardless of the actual values.

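### Do the |μA/μB| notation and the limits 0.67 to 1.5 make the lot-consistency verdict depend on which lot is in the numerator?

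*SAP*

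**What the plan says.** SAP section 2 describes the null in words as "At least 2 of the 3 vaccine lots differ by more than 1.5-fold with respect to their GMCs ratio" and then writes it as |μA/μB| > 1.5, with |μA/μB| ≤ 1.5 as the alternative. The decision rule beneath it requires the two-sided 95% CI of "the GMC ratios between each pair of the 3 lots is within the pre-defined clinical limit of [0.67, 1.5", with both limits stated. The same two limits stand in protocol 9.1 and Table 15, and in SAP 4.1.1, 4.2.2 and 5.

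On direction, protocol 9.3.1 lists "RSVPreF3_Grp1 versus RSVPreF3_Grp2, RSVPreF3_Grp1 versus RSVPreF3_Grp3, RSVPreF3_Grp2 versus RSVPreF3_Grp3", and SAP 4.2.1.1 has the same list. SAP 4.1.1 speaks of the "ratio of each lot over the each other lot is inside the acceptance limit 0.67-1.5", which can be read as all six ratios.

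On the number of tests, protocol 9.1 says "a 1-sided alpha of 2.5% will be used for the 6 non-inferiority tests" and SAP 2.1 says "A 1-sided alpha of 2.5% will be used for the 3 equivalence tests".

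On precision, SAP 6.2.4.3, under the heading on display of decimals, says "GMT or GMC group ratios and their confidence limits will be displayed with 2 decimals regardless of the actual values".

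**The concern.** This is the trial's only confirmatory criterion, so its wording deserves a literal reading. Four things look wrong on that reading.

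- Absolute bars belong on a log difference. On a ratio they leave the hypothesis one-sided: a ratio of 0.2 would satisfy the alternative.
- A 1.5-fold margin has reciprocal 0.6667, but the limit is 0.67, whose reciprocal is 1.4925. A CI of 0.668 to 0.95 for A/B fails, while the same data as B/A, about 1.05 to 1.497, pass.
- SAP 4.1.1 can be read as requiring six ratios, where SAP 4.2.1.1 lists three.
- A lower confidence limit of 0.666 prints as 0.67 and could be taken for a pass.

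If these points mattered, the verdict could turn on lot numbering or rounding, and the test might not match the margin behind the sample size.

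**Working it through.** **Inputs.** 225 evaluable per group, log10 SD 0.45, one-sided alpha 0.025, limits 0.67 and 1.5, Bonferroni over six tests (protocol 9.1 and 9.5, SAP 5). Log margins: log10(1.5) = 0.17609 and −log10(0.67) = 0.17393. SE of a difference = 0.45 × √(2/225) = 0.04243.

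**The plan's own power figure (true ratio 1).**
- Margin 1.5: 0.17609/0.04243 − 1.96 = 2.19, so beta = 1.42%. Global power = 1 − 6 × 1.42% = 91.5%.
- Margin 0.67: 0.17393/0.04243 − 1.96 = 2.14, so beta = 1.62%. Global power = 1 − 6 × 1.62% = 90.3%.
- Three tests at each limit: 1 − 3 × (1.42% + 1.62%) = 90.9%.

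The plan states 91% with a nominal beta of 1.5%. All three figures agree with it within a point and exceed the 90% target. For 90% global power, n per group is 219 at the 1.5 margin and 224 at 0.67, so 225 covers either.

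**Does the one-sided formula reach the decision?** A test of the upper limits alone would pass about 98.6% of trials with Grp3 truly 1.5-fold above the other two. The stated CI rule passes 0.4%. The rule is the test that will be run. Three equivalence tests and six one-sided tests are also the same procedure, since each pair is tested in both directions.

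**How far apart are 0.67 and 1/1.5?** With critical value 1.9635, the half-width is 1.9635 × 0.04243 = 0.0833.
- Higher lot in the numerator: the observed ratio may reach 10^(0.17609 − 0.0833) = 1.238.
- Higher lot in the denominator: it may reach 10^(0.17393 − 0.0833) = 1.232.

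**Type I error for one pair.** At a true ratio of 1.5 it is 2.5%. At a true ratio of 1/1.5, passing needs z above (0.0833 + 0.0022)/0.04243 = 2.01, which gives 2.2%. The rounding tightens the rule.

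**Joint verdict.** 4 million simulated trials per row, pooled SD, t-based CIs:

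| True state | Planned direction | Reversed | Both required | Limits 1/1.5 and 1.5 | Planned and reversed disagree |
|---|---|---|---|---|---|
| Lots equal | 92.2% | 92.2% | 91.7% | 92.6% | 0.9% |
| Grp3 1.1-fold higher | 78.2% | 79.7% | 78.1% | 79.8% | 1.7% |
| Grp3 1.2-fold higher | 44.2% | 46.4% | 44.2% | 46.4% | 2.2% |
| Grp3 1.3-fold higher | 15.0% | 16.3% | 15.0% | 16.3% | 1.4% |
| Grp3 1.5-fold higher | 0.40% | 0.47% | 0.40% | 0.47% | 0.07% |

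Disagreement arises only when a confidence limit falls between 0.6667 and 0.67, or between 1.4925 and 1.5. If all six ratios must pass, the effective limits are 0.67 to 1.4925, and the numerator cannot matter.

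**The case for a change.** The best argument for a change is that a sole primary criterion should have one reading, and that clearer wording costs almost nothing. The SAP supports both a three-ratio and a six-ratio reading. With lots equally spaced over a 1.2-fold range, joint success is 56.8% or 54.6% depending only on labelling. If someone judged success on the printed two-decimal limits, the per-pair error would rise to about 2.6 to 2.7%.

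Much of this is accurate. The formula is badly written, 0.67 is not exactly 1/1.5, SAP 4.1.1 is looser than SAP 4.2.1.1, and no sentence says that unrounded limits decide.

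The inference to a needed change does not stand:
- The labelling contrast compares the listed directions with ones nobody plans to use. The 1.2-fold spread is not a planning assumption.
- The six-ratio reading is slightly stricter and removes the dependence on the numerator altogether, so the two complaints cannot both apply.
- The two-decimal rule governs display. Nothing makes it a decision rule, and comparing unrounded limits is ordinary practice.
- Moving the lower limit to 0.6667 is more than a SAP edit. Protocol 9.1 and Table 15 carry 0.67 as a pre-defined clinical limit, and SAP 4.6 declares no departure from the protocol's analyses. The move would slightly loosen the criterion, would need confirming with the regulator, and would gain 0.4 points of power with equal lots.

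**Conclusion.** No change is needed. The absolute-value bars are a clerical slip that the explicit two-sided rule overrides. The 0.67 limit is a conventional rounding that makes the test marginally stricter. The ratio directions are fixed in advance, so one dataset gives one verdict when the listed comparisons are followed. The silence on rounding is a gap that an analyst fills by comparing unrounded limits.

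The effects are small: 92.2% against 92.6% power with equal lots, type I error at or below 2.5% per pair on unrounded limits, disagreement between directions in 0.07% to 2.2% of simulated trials, and no effect on the sample size. Even the choice between the three-ratio and six-ratio readings costs only 0.5 points of power with equal lots (92.2% against 91.7%).

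These figures assume exactly 225 evaluable participants per group, SD 0.45 with no reduction from the ANCOVA covariates, and, for power, true ratios of 1. The conclusion would differ only if the team judged success on rounded output or chose ratio directions after seeing the data, and the plan provides for neither.

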## 2.1. Multiplicity Adjustment

A 1-sided alpha of 2.5% will be used for the 3 equivalence tests.

No adjustment of Type 1 error is needed because all the Lot to Lot consistency criteria must be met simultaneously.

## 3. ANALYSIS SETS

Definition of population to be analysed:

Analysis Set	Definition / Criteria
Enrolled set	Participants who agreed to participate in a clinical study after completion of the informed consent process*.
Exposed set (ES)	All participants who received the study intervention. The analysis per group will be performed according to the administered study intervention.
Per-Protocol set (PPS)	All eligible participants who received the study intervention as per protocol, had immunogenicity results pre and post dose complied with blood draw intervals**, without intercurrent conditions that may interfere with immunogenicity and without prohibited concomitant medication/vaccination. The analysis per group will be performed according to the administered study intervention.

\*All participants enrolled and included in the database will be part of the Enrolled Set.

## 3.1. Criteria for eliminating data from Analysis Sets

Elimination codes will be used to identify participants to be eliminated from analysis. Details are provided below for exposed and per protocol sets.

## 3.1.1. Elimination from Exposed set

The following codes will be used for identifying participants to be eliminated from the Exposed set (see, Table 1):

- Code 1030 (Study intervention not administered at all)
- Code 800 (Fraudulent data)
- Code 900 (Invalid informed consent)

## 3.1.2. Elimination from Per Protocol set (PPS)

A participant will be excluded from the populations for analysis under the following conditions:

- For codes 800, 900, 1030, 1050 and 2020: participants will be eliminated for all
  visits
- For codes 1040, 1070, 1080, 1090, 2010, 2040 and 2050: participants will be eliminated from a specific visit (at which the condition is met) onwards.
- For codes 2090, 2100, 2120: participants will be eliminated at the specific visit at which the condition is met.

\*\* 30-42 days between Visit 1 and Visit 2.

Table 1 List of elimination codes

Code	Condition under which the code is used	Visit /Contact (timepoints) where the code is checked	Visit from when it is applicable	Applicable for analysis set/endpoint
800	Fraudulent data	All	All	ES and PPS for analysis of immunogenicity
900	Invalid informed consent	All	All	ES and PPS for analysis of immunogenicity
1030	Study intervention not administered at all	All	All	ES and PPS for analysis of immunogenicity
1040	Administration of concomitant vaccine(s) forbidden in the protocol Use of any investigational or non-registered product (drug, vaccine or medical device) other than the study intervention(s) during the period beginning 30 days before study intervention administration and ending 30 days after study intervention administration, or planned use during the study period.  Planned or actual administration of a vaccine not foreseen by the study protocol in the period starting 30 days before the study intervention administration and ending 30 days after the study intervention administration.  Note: In case an emergency mass vaccination for an unforeseen public health threat (e.g.: a pandemic) is recommended and/or organized by the public health authorities, outside the routine immunization program, the time period described above can be reduced if necessary for that vaccine provided it is used according to the local governmental recommendations and that the Sponsor is notified accordingly.	Visit 1,2 and contact 6 months post-vaccination	From the specific visit the condition is met	PPS for analysis of immunogenicity
1050	Randomization failure: Subject not randomized in the correct group (To be attributed by Statistician only; Check SBIR, replacement, vaccine administration)	Visit 1	All	PPS for analysis of immunogenicity
1070	Vaccine administration not according to protocol Participant was vaccinated with the correct vaccine but containing a lower volume Wrong replacement or study vaccine administered (not compatible with the vaccine regimen associated to the treatment number) Route of the study vaccine is not intramuscular Wrong reconstitution of administered vaccine	Vaccination visit 1	From the specific visit (1) the condition is met	PPS for analysis of immunogenicity

Code	Condition under which the code is used	Visit /Contact (timepoints) where	Visit from when it is	Applicable for analysis
0040		the code is checked	applicable	set/endpoint
1080	Vaccine temperature deviation Vaccine administered despite a Good Manufacturing Practices (GMP) no-go temperature deviation	Vaccination visit 1	From the specific visit (1) the condition is met	PPS for analysis of immunogenicity
1090	Expired vaccine administered	Vaccination visit 1	From the specific visit (1) the condition is met	PPS for analysis of immunogenicity
2010	Protocol violation linked to inclusion/exclusion criteria  All inclusion/exclusion criteria defined in the protocol to be checked.	Visit 1,2 and contact 6 months post- vaccination	From the specific visit (1,2) or contact (6 month) the condition is met.	PPS for analysis of immunogenicity
2020	All Pre-dose results are missing	Visit 1	All	PPS for analysis of immunogenicity
2040	Administration of any medication forbidden by the protocol Use of any investigational or non-registered drug, or medical device other than the study interventions during the period beginning 30 days before the dose of study vaccines and ending 30 days after the study intervention administration, or planned use during the study period.  Administration of long-acting immune-modifying drugs or planned administration at any time during the study period (e.g. infliximab).  Administration of immunoglobulins and/or any blood products or plasma derivatives planned administration during the study period.  Chronic administration (defined as more than 14 consecutive days in total) of immunosuppressants or other immune-modifying drugs planned administration during the study period. For corticosteroids, this will mean prednisone ≥20 mg/day, or equivalent. Inhaled and topical steroids are allowed.	Visit 1,2 and contact 6 months post-vaccination	From the specific visit (1,2) or contact (6 months) the condition is met	PPS for analysis of immunogenicity
2050	Intercurrent medical condition: Participants may be eliminated from the PPS for immunogenicity if, during the study, they incur a condition that has the capability of altering their immune response (intercurrent medical condition) or are confirmed to have an alteration of their initial immune status.	Visit 1,2 and contact 6 months post- vaccination	From the specific visit (1,2) or contact (6 months) the condition is met	PPS for analysis of immunogenicity

Code	Condition under which the code is used	Visit /Contact (timepoints) where the code is checked	Visit from when it is applicable	Applicable for analysis set/endpoint
2090	Participants did not comply with blood sample schedule: Number of days between vaccination (visit1) and blood sample (visit2) is outside [30-42] days	Visit 2	At the specific visit (2) the condition is met	PPS for analysis of immunogenicity
2100	Serological results not available at the post dose time point	Visit 2	At the specific visit (2) the condition is met	PPS for analysis of immunogenicity
2120	Obvious incoherence/abnormality or error in laboratory data Unreliable released data as a result of confirmed sample mismatch or confirmed inappropriate sample handling at lab	Visit 2	At the specific visit (2) the condition is met	PPS for analysis of immunogenicity

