5.2.2. Prior/Concomitant therapy

- Use of any investigational or non-registered product (drug, vaccine or medical device) other than the study intervention(s) during the period beginning 30 days before study intervention administration and ending 30 days after study intervention administration, or planned use during the study period.
- Planned or actual administration of a vaccine not foreseen by the study protocol in the period starting 30 days before and ending 30 days after the study intervention administration, with the exception of inactivated and subunit influenza vaccines which can be administered up to 14 days before or from 14 days after the study vaccination.

Note: In case an emergency mass vaccination for an unforeseen public health threat (e.g. a pandemic) is recommended and/or organized by the public health authorities, outside the routine immunization program, the time period described above can be reduced if necessary for that vaccine provided it is used according to the local governmental recommendations and that the Sponsor is notified accordingly.

- Previous vaccination with an RSV vaccine.
- Administration of long-acting immune-modifying drugs or planned administration at any time during the study period (e.g. infliximab).
- Administration of immunoglobulins and/or any blood products or plasma derivatives during the period starting 90 days before the administration of the study intervention or planned administration during the study period.
- Chronic administration (defined as more than 14 consecutive days in total) of immunosuppressants or other immune-modifying drugs during the period starting 90 days prior to the study intervention administration or planned administration during the study period. For corticosteroids, this will mean prednisone ≥ 20 mg/day or equivalent. Inhaled and topical steroids are allowed.

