5.5. Criteria for temporarily delaying enrolment/Study intervention administration

Enrolment/study intervention administration may be postponed within the permitted time interval until transient conditions cited below are resolved:

- Acute disease and/or fever at the time of enrolment and/or study intervention administration. Refer to the SoA (Table 1) for definition of fever and preferred location for measuring temperature in this study.
- Participants with a minor illness (such as mild diarrhea, mild upper respiratory infection) without fever may be enrolled and/or dosed at the discretion of the investigator.
- Participants with symptoms suggestive of active Coronavirus Disease 2019 (COVID-19) infection (e.g., fever, cough, etc.). The return of the participant to the site will follow the specific guidance from local public health and other competent authorities (e.g. free of symptoms, COVID-19 negative testing, etc.).
- Participants with known COVID-19 positive contacts may be vaccinated at least 14 days after the exposure, provided that the participant remains symptom-free, and at the discretion of the investigator.
- In case of administration of inactivated and subunit influenza vaccines: Postponement of study vaccine administration within given protocol timelines to allow respect of the 14-days interval between flu vaccination and study vaccine administration.

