9.2. Analysis sets

Table 14 Analysis sets

Analysis Set	Description
Enrolled Set	Participants who agreed to participate in a clinical study after completion of the
	informed consent process. *
Exposed Set (ES)	All participants who received the study intervention. The analysis per group will be
	performed according to the administered study intervention.
Per Protocol Set (PPS)	All eligible participants who received the study intervention as per-protocol, had immunogenicity results pre- and post-dose, complied with blood draw intervals (Table 2), without intercurrent conditions that may interfere with immunogenicity and without prohibited concomitant medication/vaccination. The analysis per group will be performed according to the administered study intervention.

^{*}All participants enrolled and included in the database will be part of the Enrolled Set.

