9.2.1. Criteria for elimination from analysis

If the participant meets 1 of the criteria mentioned Sections 5.2.1 (medical conditions) or 5.2.2 (concomitant therapy), he/she may be eliminated from per-protocol analysis.

Participants may be eliminated from the PPS for immunogenicity if, during the study, they incur a condition that has the capability of altering their immune response (intercurrent medical condition) or are confirmed to have an alteration of their initial immune status. Refer to Glossary of terms for the definition of intercurrent medical conditions.

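### SAP elimination code 1040 drops the protocol's influenza-vaccine exception, so the written rule for the primary analysis set does not match the protocol

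*SAP*

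**What the plan says.** **Protocol.** Section 5.2.2 excludes vaccines outside the study from 30 days before to 30 days after dosing, "with the exception of inactivated and subunit influenza vaccines which can be administered up to 14 days before or from 14 days after" study vaccination. A note lets the window be shortened for an emergency mass-vaccination campaign. Section 5.5 relies on the same influenza interval: dosing may be postponed "to allow respect of the 14-days interval between flu vaccination and study vaccine administration". Table 14 in section 9.2 limits the PPS to participants "without prohibited concomitant medication/vaccination". Section 9.2.1 ties elimination to the exclusion criteria: a participant who meets a criterion in "Sections 5.2.1 (medical conditions) or 5.2.2 (concomitant therapy), he/she may be eliminated from per-protocol analysis".

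**SAP.** Section 3 repeats the PPS definition. Table 1 in section 3.1.2 turns it into elimination codes. Code 1040 is headed "Administration of concomitant vaccine(s) forbidden in the protocol", and its stated condition includes "Planned or actual administration of a vaccine not foreseen by the study protocol in the period starting 30 days before the study intervention administration"; the window closes 30 days after dosing. The emergency-vaccination note follows; the influenza exception does not. For this code, "participants will be eliminated from a specific visit (at which the condition is met) onwards". Section 4.2.2 makes the PPS the primary analysis set, and section 4.6 records no change to the protocol-defined analyses.

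**The concern.** The elimination table is what a programmer works from when building the PPS. Code 1040 reproduces one protocol relaxation and omits the other, so the list in the cell can be taken as complete. Applied as written, a permitted influenza vaccination would trigger the code at Visit 1 (given before dosing) or by Visit 2 (given after dosing). Either way the Day 31 result, which is the primary endpoint, is lost.

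The primary estimand in SAP 1.1 concerns eligible participants who followed the protocol, so the literal rule removes people the estimand is meant to include. The likely cost is avoidable loss of precision. There is also a procedural cost: if the SAP and the protocol give different PPS membership, someone must choose between them, and that choice should not be made after unblinding.

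**Working it through.** **Step 1: compare the two texts.**

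| Element | Protocol 5.2.2 | SAP code 1040 |
|---|---|---|
| Vaccines not provided for in the protocol, 30 days before to 30 days after dosing | Yes | Yes |
| Emergency mass-vaccination note | Yes | Yes |
| Inactivated and subunit influenza vaccines under a 14-day rule | Yes, in the same sentence as the restriction | Absent |

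**Step 2: look for text that restores the exception.**
- No other SAP section restates it.
- The restriction is limited to vaccines the protocol did not foresee, but the protocol uses that same limiter and still adds an express exception. The limiter alone therefore does not clearly exempt influenza vaccines.
- Code 2010 checks all protocol eligibility criteria, but it is a separate ground for elimination. Passing it does not cancel a 1040 flag.
- The heading of code 1040 does point back to what the protocol forbids. Heading and condition then disagree within one table cell.

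**Step 3: affected window.** The protocol permits these influenza vaccines from day 14 outwards on either side of dosing, while code 1040 reaches to day 30. Counting both ends, 30 − 14 + 1 = 17 days on each side.

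**Step 4: reproduce the plan's power.** Inputs from SAP section 5: SD 0.45 (log10), upper margin 1.5, one-sided alpha 0.025, 225 evaluable per group, six tests. Equal lots are assumed.
- Margin: log10(1.5) = 0.1761.
- Standard error: 0.45 × √(2/225) = 0.0424.
- Noncentrality: 0.1761 / 0.0424 = 4.15, with 2 × 225 − 2 = 448 degrees of freedom.
- Type II error per test (noncentral t): 1.46%, against the plan's 1.5%.
- Global power: 1 − 6 × 1.46% = 91.3% before rounding of the error, against the plan's 91%.
- Enrolment: 225 / 0.90 = 250 per group, as planned.

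**Step 5: illustration only.** The documents give no influenza-vaccination rate. The losses below are assumptions, taken on top of the planned 10%. The simulation used three equal lots and required all three 95% intervals inside [0.67, 1.5]. Neither power column credits the baseline covariate.

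| Assumed extra loss | Evaluable per group | Plan's method | Simulation |
|---|---|---|---|
| None | 225 | 91.3% | 92.2% |
| 5% (213.75, taken as 214) | 214 | 1 − 6 × 1.88% = 88.7% | 90.1% |
| 10% (202.5, taken as 202) | 202 | 1 − 6 × 2.48% = 85.1% | 87.3% |

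By the plan's method, 220 per group still gives 90.2% and 219 gives 89.9%. The planned ANCOVA adjusts for baseline, which reduces the residual SD to 0.45 × √(1 − r²). With an assumed baseline to Day 31 correlation of 0.3, the plan's method gives 93.1% at 214 and 90.6% at 202.

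**The case against.** The best defence is that nobody intended a stricter rule. The heading of code 1040, the PPS definitions in both documents, protocol 9.2.1, the estimand and the empty SAP 4.6 all point to the protocol as the governing text. Table 1 is condensed elsewhere too: code 2040 refers to "Administration of immunoglobulins and/or any blood products or plasma derivatives planned administration during the study period" and leaves out the 90-day look-back in protocol 5.2.2. A careful programmer could reach the protocol-consistent result. No harm has been quantified either. Any loss may fit within the 10% allowance, and section 4.2.2 adds an Exposed Set analysis if more than 5% of vaccinated participants with results are left out of the PPS in any group.

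Most of this stands. It supports reading the gap as one omitted clause, with no proof that anyone will be wrongly removed, and it means the power illustration should carry no weight in rating the point. It does not remove the mismatch. The surrounding text shows what was meant, but the stated condition still says something else. The Exposed Set analysis complements the PPS result and does not correct PPS membership.

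**Conclusion.** The inconsistency is real and minor. The wording mismatch is certain, because it rests only on comparing the two texts. Its effect is uncertain: it depends on whether code 1040 is applied to the letter and on how many participants had a permitted influenza vaccine in the 17-day window on either side of dosing. The documents settle neither.

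Bias between lots is unlikely, since lots are randomized and blinded and the rule is the same for all three. Over-exclusion does not make a false claim of consistency easier. What remains is an ambiguous membership rule for the primary analysis set and a possible, unquantified loss of precision.

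**What to change.** Before unblinding for the final analysis, reconcile code 1040 with protocol 5.2.2. Either copy the protocol's existing influenza-vaccine exception into the code or replace the restated condition with a cross-reference to 5.2.2. Then check that the derivation flags only vaccinations the protocol prohibits. No clinical rule changes, and no view is taken here on the interval itself.

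The cost is one clause in the SAP table and one check of the derivation. Dates are already collected: protocol 8.2.1.3 records vaccines from the year before dosing, with influenza formulation, and section 6.8 records vaccinations in the 30 days after. Section 6.8 does not specify vaccine type, so confirm while blinded that the recorded product identifies an inactivated or subunit influenza vaccine given after dosing.
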